This study will assess the benefit to both the patient and health care system by allowing patients to safely undergo outpatient or short-stay Total Knee Arthroplasty (TKA) with improved postoperative pain and function with a short-duration tourniquet treatment protocol which includes the FDA-approved Aquamantys Bipolar sealer (Medtronic, Minneapolis, MN). The Aquamantys Bipolar Sealer is a single use, sterile, bipolar device intended to be used in conjunction with the Aquamantys Pump Generator for delivery of radiofrequency (RF) energy and saline for hemostatic sealing and coagulation of soft tissue and bone at the operative site. It is intended for, but not limited to orthopaedic, spine, thoracic and open abdominal surgery.

This study will provide invaluable information for both surgeons and hospital administrators to use when comparing potential treatment options for knee arthroplasty patients, with the end goal of making clinically meaningful improvements to patient care. It will also highlight the clinical importance of maintaining early quadriceps function. Quadriceps dysfunction has been linked to the amount of postoperative swelling (Holm et al., Arch Phys Med Rehabil, 2010). Anecdotally, we have seen a dramatic reduction in the amount of swelling present at the patient's first physical therapy visit on the day of surgery when utilizing a short-duration tourniquet protocol including the Aquamantys. By using Aquamantys to minimize effusion as part of a tourniquet-less TKA protocol, patients may be able to avoid loss of quadriceps function, which may then provide both short- and long-term benefit. Tourniquet-less TKA may reduce complications and readmissions by theoretically reducing fall risk by maintaining quadriceps function. Improved quadriceps function not only reduces fall risk but may allow patients to more rapidly achieve functional milestones after surgery such as walking without an assistive device and navigating stairs.

Objectives

List your research objectives. Please include a summary of intended research objectives in the box below.

The specific goals of study are to compare quadriceps strength, pain, opioid consumption, and patient function during the first three months in the setting of short-stay TKA between patients treated with short-duration tourniquet TKA with the Aquamantys® bipolar sealer versus those treated with the standard of care (tourniquet used throughout the case and no Aquamantys®).

Study Design

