In order to determine an appropriate sample size, an a priori power analysis was performed. We chose to use isometric quadriceps strength at two weeks as the primary outcome variable. Using an alpha level of 0.05 and the standard deviation and minimal clinically important difference reported by Husted et al. (Trials, 2018) of 0.22 Nm/kg and 0.15 Nm/kg, respectively, a sample size of 70 total patients (35 patients per group) would be 80% powered to detect clinically important differences (G*Power, version 3.1).

Data collection will coincide with four regularly-scheduled patient visits: preoperative and 2, 6, and 12 weeks after surgery. Participants will complete isometric quadriceps testing at each study visit, and will be asked to complete the KOOS,JR, VR-12, and VAS pain scale questionnaires. We will also record the participant's opioid consumption per our standard of care, as well as whether the patient is able to walk without an assistive device and/or self-reports the ability to navigate stairs. Beginning at the 6-week postoperative visit, patients will be asked to complete the five times sit-to-stand test. The primary outcome variable, isometric quadriceps strength at 2 weeks, will be compared between groups using a two-tailed independent t-test. All continuous secondary variables will be assessed using group x time repeated measures ANOVAs. The prevalence of patients that can walk without an assistive device and/or navigate stairs at 2, 6, and 12 weeks will be compared between groups using chi-square or Fisher Exact tests as appropriate.

Attachments

Subject Recruitment Methods & Advertising

Describe how the study team will identify and recruit subjects. Please consider the following items and provide additional information as needed so that the IRB can follow each step of the recruitment process.

- How will the study team identify potential participants?
- Who will first contact the potential subjects, and how?
- Will you use advertisements? If so, how will you distribute those?
- How and where will the research team meet with potential participants?
- If applicable, describe proposed outreach programs for recruiting women, minorities, or disparate populations.
- How you will minimize undue influence in recruitment?
- Attach copies of all recruiting and advertising materials (emails, verbal scripts, flyers, posts, messages, etc.).

For additional information on recruiting and advertising:

- [IRB Application Instructions - Advertisements](#)

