Five Times Sit-to-Stand Test: The five-repetition sit-to-stand is commonly used to measure mobility and function in older adults. Participants are positioned in a standard 16" office chair with their arms at their sides and back located against the back of the chair. Participants are instructed to "Please stand up straight as quickly as you can 5 times, without stopping in between. Keep your arms folded across your chest. I'll be timing you with a stopwatch. Ready, begin." The test is timed using a stopwatch and the timer is stopped when the individual achieves a standing position on the 5th trial. To ensure safety, we will utilize a four-legged chair that does not have wheels, and the chair will be placed so it backs against a wall to prevent the chair from moving during the test. While the participant will be asked to complete the test without using the chair's armrests, the armrests are available for balance should they need assistance. If at any visit the participant cannot complete one practice repetition of sit to stand without using the armrests, we will not ask them to participate in the test at that visit.

Patient-Reported Outcomes: Participants will be asked to complete four questionnaires at each study visit. Participants will be asked to complete the Knee injury and Osteoarthritis Outcome Score, Joint Replacement (KOOS JR) questionnaire which is a 7-item instrument validated to assess patient outcomes following knee arthroplasty. Other questionnaires will include the Veterans Rand-12 (VR-12) which is a 12-item instrument that assesses physical and mental health and a Visual Analogue Scale (VAS) to assess pain and patient confidence in their knee. In addition, a study-specific questionnaire will be used to assess whether the patient is able to ambulate without an assistive device and to determine the method by which the patient navigates stairs (one-step at a time, requires the use of a handrail, etc.).

Attachments

Attach Type	File Name
ResearchProcedures	Aquamantys Page 4 Study Flow Chart.pdf

Data Collection & Research Materials

In this section, please provide the following:

- Describe all sources or methods for obtaining research materials about or from living individuals (such as specimens, records, surveys, interviews, participant observation, etc.), and explain why this information is needed to conduct the study.

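### The planned ANOVA for continuous secondary outcomes is valid but does not use the preoperative values as a covariate, and sit-to-stand has no stated way to count patients who cannot do the test

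*Combined protocol and SAP*

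**What the plan says.** The aim, under Objectives, is broad: "The specific goals of study are to compare quadriceps strength, pain, opioid consumption, and patient function during the first three months". Under Study Design, the schedule is "Data collection will coincide with four regularly-scheduled patient visits: preoperative and 2, 6, and 12 weeks after surgery". Strength is tested each time ("Participants will complete isometric quadriceps testing at each study visit"), and Research Procedures adds "Participants will be asked to complete four questionnaires at each study visit". Strength, KOOS JR, VR-12 and VAS therefore all have a preoperative value and three postoperative ones. Sit-to-stand differs: "Beginning at the 6-week postoperative visit, patients will be asked to complete the five times sit-to-stand test".

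The primary analysis is separate: "The primary outcome variable, isometric quadriceps strength at 2 weeks, will be compared between groups using a two-tailed independent t-test". Every other continuous outcome falls under one sentence: "All continuous secondary variables will be assessed using group x time repeated measures ANOVAs". It names no covariate. It does not say whether the preoperative visit is a level of time, which term is decisive, or what estimates will be reported.

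The Five Times Sit-to-Stand paragraph says that a patient who cannot manage one practice repetition without the armrests is not tested at that visit. Potential Risks & Benefits says the same of functional testing judged unsafe. Neither says how such patients enter the analysis.

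**The concern.** Pain and function over three months are stated goals, and their continuous measures rest on that one sentence. If the preoperative visit is a level of time, the interaction uses it only as change from baseline, that is, with the slope on baseline fixed at 1. If time means the postoperative visits only, the preoperative values go unused. Either way precision is given up that costs nothing to obtain. An interaction test also does not by itself say how large the benefit is at each visit.

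Sit-to-stand raises two further points. With only two postoperative visits, a benefit that is equal at both is by definition not an interaction. And the patients who are not tested are missing because of poor function, which is what the test measures. A method that assumes data are missing at random does not cover that.

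**Working it through.** **Inputs.** From Study Design: 35 per arm, alpha 0.05 two-sided, strength SD 0.22 and MCID 0.15 Nm/kg, visits preoperatively and at 2, 6 and 12 weeks. Assumed, because the documents do not give them: unit variance, equal correlation ρ between all visits (0.3/0.5/0.7), complete data, and a 0.5 SD effect. The 0.68 SD implied for 2-week strength is used as a second value.

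**1. The plan's own figure.** 0.15/0.22 = 0.68 SD. Noncentrality 0.682 × √(35/2) = 2.85 on 68 df gives 80.3% power. N = 70 is reproduced.

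**2. Precision at one visit.** The standard errors of a group difference, in SD units, are:
- unadjusted: √(2/35) = 0.239
- change from baseline: √(4(1−ρ)/35) = 0.283/0.239/0.185
- adjusted: √(2(1−ρ²)/35) × √(68/67) = 0.230/0.209/0.172, where the last factor allows for chance imbalance in the preoperative value.

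Multiplying by the t quantile (about 2.00) gives 95% half-widths of 0.477 unadjusted, 0.564/0.477/0.369 for change and 0.459/0.416/0.343 adjusted. Adjusted is 19/13/7% narrower than change and 4/13/28% narrower than unadjusted. This does not depend on the shape of the effect.

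**3. Like-for-like 3-df tests**, with the preoperative visit as a level of time. Let δ be the effects at 2, 6 and 12 weeks.
- ANOVA interaction: λ = (35/2)[Σδ² − (Σδ)²/4]/(1−ρ), F on 3 and 204 df.
- Joint test of the three adjusted differences: λ = (35/2)[Σδ² − ρ(Σδ)²/(1+3ρ)]/(1−ρ) × 67/68, F on 3 and 65 df.

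Because ρ/(1+3ρ) is below 1/4 for any ρ below 1, the adjusted bracket is never the smaller. Example, ρ = 0.5 and 0.5 SD constant: Σδ² = 0.75 and (Σδ)² = 2.25, so λ = 6.56 for the interaction and 10.5 × 67/68 = 10.3 for the adjusted test.

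| Effect at 2, 6, 12 weeks (SD) | Interaction power, ρ 0.3/0.5/0.7 | Adjusted joint power |
|---|---|---|
| 0.5, 0.5, 0.5 | 41/55/79% | 72/75/87% |
| 0.5, 0.25, 0 | 38/51/75% | 46/55/76% |
| 0.68, 0.68, 0.68 | 69/84/98% | 95/96/99% |
| 0.68, 0.34, 0 | 64/80/96% | 74/84/97% |

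A late effect (0, 0.25, 0.5) gives the same results as the fading one. The unequal-correlation case (0.3 with the preoperative value, 0.7 between postoperative visits, 0.5 SD), by simulation, gives interaction against adjusted 49.5 v 50.2% for a constant effect and 50.3 v 67.5% for a fading one. The gain is therefore not tied to one shape.

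An adjusted average over the postoperative visits has only 34/36/44% power for the fading effect (simulated), below the planned interaction.

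**4. Sit-to-stand, which term.** With two visits the interaction is the group difference in 12-week minus 6-week change. A constant benefit makes it zero, so it rejects 5% of the time at any ρ. The group effect averages the two visits, with SD √((1+ρ)/2). For 0.5 SD its power is 72/66/61%.

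**5. Sit-to-stand, inability.** Illustration: true difference 0.50 SD, and a patient is untested below a common performance threshold.
- 10% of controls unable: threshold −1.282. Share unable in the other arm: Φ(−1.282 − 0.5) = 3.7%.
- Mean among tested controls: 0.1755/0.90 = 0.195. Mean in the other arm: 0.5 + 0.0816/0.963 = 0.585.
- Difference among those tested: 0.585 − 0.195 = 0.39 SD.
- With 20% of controls and 9.0% of the other arm unable, it is 0.33 SD.

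By simulation (4,000 runs), power for the tested-only 6-week comparison falls from 55% to 42% (34% in the second case). Ranking patients who are unable as worst keeps 51% in both.

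**The case against.** The strongest reply is that no analytic error is shown. The ANOVA is valid, the outcomes are secondary and the text is one paragraph on an IRB form. Its silence on contrasts and CIs does not mean that only p-values will be reported. That stands: a reader might infer that the plan excludes estimates by visit, but the documents do not say so.

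A reader might also infer that the sit-to-stand analysis cannot work. It can. The same ANOVA yields a group effect with 61–72% power for a constant 0.5 SD benefit, and nothing names the interaction as decisive. Leaving the term unnamed is missing detail, not a failed test.

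The large power gap needs a constant effect. The background and Research Procedures stress early function, although longer benefit is mentioned too. For a fading effect at 0.5 SD the gain is 8, 4 and 1 points. Study Design also implies a larger effect, 0.68 SD, for 2-week strength. There both tests are stronger, and at ρ of 0.5 or above the constant-effect gap shrinks from 20 and 8 points to 12 and 2, while the fading gap stays at about 4 points or less.

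Finally, attenuation from untested patients is not automatic. It needs inability to follow performance and to differ by arm, and the rates used are assumed. Eligibility requires patients able to complete study procedures, which may lower the rate but does not exclude inability after surgery.

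**Conclusion.** The point holds as an improvement that costs almost nothing, not as a flaw that invalidates a test. Under equal correlation, the baseline-adjusted CI is 19/13/7% narrower than change from baseline and 4/13/28% narrower than unadjusted. The power gain over the interaction runs from 31 points (constant 0.5 SD, ρ = 0.3) to about 1 point or less (fading, ρ = 0.7). The 0.68 SD rows are a benchmark, because the plan gives that value for strength at 2 weeks only. For sit-to-stand, non-testing for poor function needs its own prespecified handling. The fall from 0.50 to 0.39 SD shows what could happen and is not a forecast. Opioid consumption, recorded as "opioid consumption per our standard of care", is outside the covariate point because no preoperative value is clearly stated. The primary t-test and N = 70 are unaffected.

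**What to change.** **KOOS JR, VR-12, VAS, and strength at 6 and 12 weeks.** Replace the ANOVA with a mixed model on the postoperative visits: group, visit, group by visit, preoperative value and preoperative value by visit. Report the adjusted group difference with its 95% CI at each visit. Make the joint test of those differences the main test for each outcome, because the timing of benefit is uncertain. For strength, that test covers 6 and 12 weeks only, and the planned t-test stays the sole test of the 2-week primary outcome.

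**Sit-to-stand.** Test the group difference at 6 and at 12 weeks. Prespecify an added analysis that ranks patients unable to do the test as worst, or one that compares able against unable by arm. Report the numbers not tested, with reasons, by arm. The rules on when to test need not change.

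**Cost.** Slightly more analysis work and one extra recorded reason for each missed sit-to-stand test. No new visits, measurements or patients.

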Describe why potential benefits are reasonable in relation to potential risks. If applicable, justify why risks to vulnerable subjects are reasonable to potential benefits.

Aquamantys Bipolar Sealer: Delicate body structures could be damaged by hot saline run-off. We will use proper suctioning and other protective measures during surgery to reduce this risk.

Isometric Quadriceps Strength and Sit-to-Stand Testing: The possible risks for participation in this study are minimal. Participants may injure their leg during the performance of the functional testing; however, all precautions will be taken to prevent this. All functional testing will be carried out by a trained member of the research team. It is also possible that some participants may experience muscle soreness following the strength and functional testing. However, this soreness will not be significantly greater than that which they may experience in response to starting a new exercise during physical therapy. If the functional testing is deemed unsafe for the participant to complete they will not complete the testing at that session.

Participation in the study may not result in any benefits to participants. This study may help doctors better understand different materials used in hip replacements that may help others in the future.

Available Alternative Opportunities/Treatments

Describe alternative treatments or opportunities that might be available to those who choose not to participate in the study, and which offer the subject equal or greater advantages. If applicable, this should include a discussion of the current standard of care treatment(s).

There are no alternative treatments to this study other than not participating in this study. The participant may receive either short or long duration tourniquet use without being in the study as both methods of surgery are currently utilized.

[Back to Top](#)

Records, Privacy, and Confidentiality

Specify where the data and/or specimens will be stored and how the researcher will ensure the privacy and confidentiality of both. Specify who will have access to the data/specimens and why they need access.

Describe how data will be managed after the study is complete:

- If data/specimens will be maintained, specify whether identifiers will be removed from the maintained information/material.
- If identifiers will not be removed, provide justification for retaining them and describe how you will protect confidentiality.

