Yes No

Payment

Describe the incentives (monetary or other) being offered to subjects for their participation. If monetary compensation is offered, indicate the amount and describe the terms and schedule of payment. Please review [this guidance](#) for more information on payments to subjects, including restrictions and expectations.

Participants will be paid \$50.00 following for taking part in this study. Payment will be prorated and participants will receive \$12.50 for each of the four study visits. Payment will be received in the form of a check 3-4 months after the surgery.

Costs to Subjects

Include a list of services and/or tests that will not be paid for by the sponsor and/or the study (e.g., MRI, HIV). Keep in mind that a subject will not know what is "standard" – and thus not covered by the sponsor/study – unless you tell them.

Participants and/or their insurance company, Medicare, or Medicaid will be responsible for the costs of all care and treatment that they would normally receive for any conditions they may have. These are costs that are considered medically necessary and will be part of the care participants receive even if they do not take part in this study.

The University of Kentucky may not be allowed to bill the participant's insurance company, Medicare, or Medicaid for the medical procedures done strictly for research.

The following costs will be paid for by the study:

- Isometric quadriceps testing
- Sit-to-stand test
- KOOS JR Questionnaire
- VR-12 questionnaire
- VAS pain scale.
- Functional questionnaire

In Case of Study Related Injuries: Salient Surgical Technology, Inc., received FDA 510K clearance on Aug 29, 2011 (see appendix A). On July 11, 2011, Medtronic acquired Salient Surgical Technologies (see appendix B). This device is being used for an approved indication and is not considered investigational to this study. The use of this device is also part of the investigator's standard of care. Either the participant or their insurance will be billed for the costs of the medical care.

Data and Safety Monitoring

The IRB requires review and approval of data and safety monitoring plans for greater than minimal risk research or NIH-funded/FDA-regulated clinical investigations.

- If you are conducting greater than minimal risk research, or your clinical investigation is NIH-funded, describe your Data and Safety Monitoring Plan (DSMP). [Click here for additional guidance on developing a Data and Safety Monitoring Plan](#).

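### The repeated measures ANOVA for continuous secondary outcomes has no rule for partial records and, as usually run, drops a participant from an outcome when one visit is missing

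*Combined protocol and SAP*

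**What the plan says.** All references are to the combined protocol and SAP.

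- **Study Design, visits.** "Data collection will coincide with four regularly-scheduled patient visits: preoperative and 2, 6, and 12 weeks after surgery". For one test the series is shorter: "Beginning at the 6-week postoperative visit, patients will be asked to complete the five times sit-to-stand test".
- **Study Design, analysis.** "All continuous secondary variables will be assessed using group x time repeated measures ANOVAs". The primary outcome is handled separately: "isometric quadriceps strength at 2 weeks, will be compared between groups using a two-tailed independent t-test". Walking without an assistive device and navigating stairs are compared at 2, 6 and 12 weeks by chi-square or Fisher tests.
- **Research Procedures, Five Times Sit-to-Stand Test.** If a participant cannot do one practice rise without the armrests, "we will not ask them to participate in the test at that visit".
- **Potential Risks & Benefits.** For strength and sit-to-stand testing: "If the functional testing is deemed unsafe for the participant to complete they will not complete the testing at that session".
- **Payment.** Payment is prorated by visit, so partial attendance is provided for.

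No section supplied gives a mixed model, imputation, an available-case rule, an analysis population, or a rule for withdrawals and missed visits.

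**The concern.** The procedures treat non-completion one session at a time: a participant who skips a test is tested again at the next visit. The named analysis, as usually implemented, works on whole records. It needs a value at every time level, so one empty visit removes that participant's other values for the same outcome. For example, a patient who cannot do the sit-to-stand test at 6 weeks but gives a valid time at 12 weeks would have the 12-week time left out. A patient who withdraws after 6 weeks would contribute nothing to the KOOS JR, VR-12 or VAS analyses.

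Strength, pain and function over three months are stated objectives, and their continuous secondary comparisons rest on this method. At stake are lost precision, a set of analysed patients that changes from outcome to outcome, and possible bias if those who drop out differ by arm in their earlier results.

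**Working it through.** **1. The plan's own figure.** Inputs from Study Design: SD 0.22 Nm/kg, difference 0.15 Nm/kg, alpha 0.05, two-sided test, 80% power. The standardised difference is 0.15/0.22 = 0.682. The noncentral t calculation gives 34.75, so 35 per group and 70 in total, with power 80.3%. The figure reproduces and contains no allowance for loss. The stated maximum of 73 leaves a margin of 3/73 = 4.1%, which is not described as a dropout allowance.

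**2. Which analyses are exposed.**

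| Event | Analyses affected under complete-case ANOVA |
|---|---|
| Strength test skipped at one session | Strength over time only |
| Sit-to-stand skipped at one session | Sit-to-stand only |
| Visit missed, or withdrawal | Every continuous outcome due at the missing visits |
| Any of these | Not the 2-week t-test through this mechanism; not the per-visit walking and stairs tests |

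**3. Participants lost.** No missing rate is given, so a rate m per postoperative visit is assumed, with a complete baseline. For k visits that can be missed:

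- same people miss every time: 70m
- independent misses: 70[1 − (1 − m)^k]
- no overlap: 70km

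| Outcome | m | Same people | Independent | No overlap |
|---|---|---|---|---|
| Three postoperative visits | 5% | 3.5 | 70(1 − 0.857) = 10.0 | 10.5 |
| Three postoperative visits | 10% | 7 | 70(1 − 0.729) = 19.0 | 21 |
| Sit-to-stand, two visits | 5% | 3.5 | 70(1 − 0.9025) = 6.8 | 7 |
| Sit-to-stand, two visits | 10% | 7 | 70(1 − 0.81) = 13.3 | 14 |

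**4. Collected values discarded (four-visit outcome).** Under independence, values collected are 70[1 + 3(1 − m)] and values used are 4 × 70(1 − m)^3.

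- m = 5%: 269.5 collected, 240.1 used, 29.4 discarded (11%).
- m = 10%: 259.0 collected, 204.1 used, 54.9 discarded (21%).
- If the same 10% miss all three postoperative visits, only their 7 baseline values are discarded: 7/259 = 2.7%.

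**5. Precision.** Simply using everyone observed at a visit, against complete cases only, gives a standard error ratio of √[(1 − m)/(1 − m)^3] = 1/(1 − m): 1.05 at 5% and 1.11 at 10%. A likelihood model also draws on correlated visits. In simulation (35 per arm, four visits, assumed correlation 0.6, independent misses, 1,500 runs), complete-case standard errors were 5–8% larger at m = 5% and 13–18% larger at m = 10%. The 18% is for the baseline difference; the postoperative visits gave 13–16%. Neither method was biased when missingness was completely at random. If misses fall entirely on the same people, this loss nearly vanishes, because complete and available cases then coincide at each postoperative visit.

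**6. Bias.** One assumed mechanism let dropout after week 2 depend on a low week-2 value in the control arm only, leaving about 57 of 70 completers. A true 12-week difference of 0.50 SD averaged 0.36 SD in complete cases and 0.51 SD in the likelihood model. The complete-case baseline difference also shifted, to −0.14 SD, so the 12-week change from baseline was almost intact: 0.36 + 0.14 = 0.50. The 2-week change was not: 0.26 + 0.14 = 0.40 against 0.50. With milder dropout (about 11–12% lost overall), a true 12-week difference of 0.30 SD averaged 0.23–0.28 SD in complete cases. The answer depends on the mechanism and the contrast, and the documents give no basis for choosing a mechanism.

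**The case against.** The plan never says complete cases only and names no software. A group by time analysis can be fitted with a mixed procedure that keeps partial records, so deletion is inferred from the usual implementation. That is right, and the point is worded accordingly. Nothing in the plan points to the mixed procedure either, and one sentence would settle it.

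Eligibility requires that participants can attend follow-up and complete study procedures and questionnaires, and visits coincide with routine care, so losses may be small. They may also cluster in the same people, in which case independence gives counts near the maximum. Both stand, which is why a range is shown.

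The simulated dropout depends on earlier observed values, a setting that favours a likelihood model. The skips the protocol describes depend on inability or safety at the same visit, which is plausibly not missing at random. This also stands: the mixed model recovers discarded values but is not shown to remove bias from those skips.

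A reader might infer several stronger things that the documents do not support:

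- **The primary result is weakened.** It is not: a t-test at 2 weeks is untouched by later gaps.
- **All function results rest on the ANOVA.** Walking and stairs do not.
- **One skipped test removes a participant from every outcome.** It affects that outcome only.
- **A real benefit would be understated.** That assumes both a benefit and a particular dropout pattern.

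**Conclusion.** The concern holds for the continuous secondary outcomes. The named method, as conventionally run and with no rule to the contrary, sets aside values already collected. The expected cost is mainly precision: roughly 5–18% on standard errors at 5–10% missed per postoperative visit, assuming independent misses and a within-person correlation of about 0.6, and less if misses cluster. Bias is possible if loss depends on earlier observed results, but its size and direction cannot be fixed from the documents. This is a worthwhile, inexpensive improvement to the secondary analyses and does not threaten the primary comparison.

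**What to change.** In Study Design, replace the repeated measures ANOVA with a likelihood-based mixed model for repeated measures, with terms for group, visit and group by visit. Fit it to every observed value of every randomised participant in the assigned group. State that a skipped session, missed visit or withdrawal does not remove values from other visits, and that a 12-week sit-to-stand time is kept when the 6-week test was not done. The covariance structure and degrees-of-freedom method can be left to the statistician.

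The cost is a sentence or two and standard software, with no new data, visits or participants and no change to the testing rules. With complete data the two approaches give essentially the same answer. The downside is reliance on missing at random, which is weaker than the missing-completely-at-random condition that complete-case ANOVA generally needs. The plan would still have to say separately how tests skipped because the patient was unable or unsafe at that visit are to be treated.

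### Preoperative walking-aid and stairs status is collected but not used in the planned chi-square/Fisher comparisons: a missed efficiency in secondary outcomes, not an error

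*Combined protocol and SAP*

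**What the plan says.** The statistical paragraph of Study Design names the outcome as "The prevalence of patients that can walk without an assistive device and/or navigate stairs" and says that it "at 2, 6, and 12 weeks will be compared between groups using chi-square or Fisher Exact tests as appropriate". It names no covariate, no stratification factor and no model across visits for these outcomes.

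The same section sets the schedule: "Data collection will coincide with four regularly-scheduled patient visits: preoperative and 2, 6, and 12 weeks after surgery". Under Research Procedures, Patient-Reported Outcomes, the protocol adds: "Participants will be asked to complete four questionnaires at each study visit". The instruments described there are the KOOS JR, the VR-12, the VAS and a fourth form: "a study-specific questionnaire will be used to assess whether the patient is able to ambulate without an assistive device". That form also serves "to determine the method by which the patient navigates stairs".

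The preoperative visit is one of the four, and the study-specific form is one of the four questionnaires. Preoperative walking-aid and stairs status is therefore collected. The plan gives no reason for leaving it out of the analysis. It also gives no expected rates, no baseline-to-follow-up association and no power for these outcomes.

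**The concern.** Patient function is one of the four goals under Objectives. The background text names walking unaided and managing stairs as the milestones that better quadriceps function should bring sooner, so these outcomes bear directly on the trial's rationale.

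With 35 patients per arm, a raw two-by-two comparison has limited power for anything short of a large difference. If preoperative status predicts later status, ignoring it leaves explainable variation in the comparison. A chance difference between arms before surgery also goes unaddressed in the estimate. What is at stake is the precision of a secondary comparison, not the trial's primary conclusion.

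**Working it through.** **1. The plan's own figure.** The inputs are in Study Design: SD 0.22 Nm/kg, difference 0.15 Nm/kg, alpha 0.05, two-sided test, 80% power.

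- Normal approximation: n per arm = 2 × (1.960 + 0.842)² × (0.22/0.15)² = 2 × 7.85 × 2.151 ≈ 33.8, so 34.
- Noncentral t: power is 79.1% at 34 per arm and 80.3% at 35.

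The stated 35 per arm (70 in total) reproduces. It concerns quadriceps strength at 2 weeks only.

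**2. Unadjusted chi-square at 35 per arm.** The rates are assumptions. With p̄ the mean of the two rates, power = Φ{[|p₁ − p₀|√n − 1.96√(2p̄(1 − p̄))] / √(p₀(1 − p₀) + p₁(1 − p₁))}.

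- For 50% v 80%: (0.3 × 5.916 − 1.96 × 0.6745) / 0.6403 = (1.775 − 1.322) / 0.6403 = 0.707, so power is about 76%.
- The same formula gives 38.5% for 40% v 60%, 72.2% for 40% v 70% and 55.4% for 70% v 90%.

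**3. Stratifying on preoperative status.** Simulated trials had 35 per arm, one visit and a two-sided 0.05 test. Preoperative and follow-up status were dichotomised from correlated normal variables. Rates and correlations are assumptions.

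| Rates able; preoperatively able | Latent correlation | Chi-square | CMH |
|---|---|---|---|
| 50% v 80%; 50% | 0.4 (phi about 0.24) | 77% | 78% |
| 50% v 80%; 50% | 0.6 (phi about 0.37) | 78% | 82% |
| 50% v 80%; 50% | 0.8 (phi about 0.52) | 77% | 89% |
| 75% v 95%; 70% | 0.6 | 71% | 73% |

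These rows are from 4,000 trials each, so each entry has a simulation error of about √(0.77 × 0.23 / 4000) ≈ 0.7 points. A further set of runs gives the change relative to chi-square as:

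- about -2 points at correlation 0 to 0.2;
- 0 to +1 at 0.4;
- +2 to +5 at 0.6;
- +8 to +11 at 0.8.

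The 12-point gap in the third table row agrees with the last range within simulation error and rounding.

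**4. Sensitivity to the assumed rates.** A separate simulation (20,000 trials per scenario; 40% v 60%, 40% v 70% and 70% v 90%) indexed the association by phi between the two binary answers. The gain of CMH over chi-square was about -0.5 to +1 point at phi 0, 1 to 3 at 0.2, 3 to 5 at 0.3, 7 to 9 at 0.4 and 11 to 13 at 0.5. The pattern is the same, with somewhat larger gains at these rates.

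**5. Type I error.** Under no effect, CMH rejected in 3.2% to 5.1% of trials, including when 90% or 95% of patients are able. A likelihood-ratio test from logistic regression adjusted for preoperative status rejected in 5.7% (50% able), 5.8% (80%), 6.9% to 7.0% (90%) and 7.5% to 8.8% (95%). Uncorrected chi-square in the same runs gave 3.4% to 5.6%.

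**6. Chance imbalance.** Assuming simple randomisation, the probability of a preoperative difference of at least 15 percentage points is about 19% if half are able and about 15% if 70% are able. For at least 20 points it is about 12% and 9%.

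**The case against.** The strongest reply is that nothing here is wrong. Chi-square and Fisher tests are valid under randomisation, their error rate already allows for chance imbalance, and the outcomes do not drive the sample size. That stands.

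Second, the gain is conditional. The documents do not say that patients who need an aid before surgery tend to need one afterwards; the background text ties early milestones to swelling and quadriceps function after surgery. With weak prediction, stratifying gains nothing and may lose a point or two. That also stands.

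A reader might infer that power is being lost for no reason, or that adjustment would lift power from the high 60s to about 90%. The documents support neither. The first needs an association that they do not report. The second takes Fisher as the planned test and assumes a correlation near 0.8. The plan allows either test as appropriate; at 50% v 80% the smallest expected count is 35 × 0.35 ≈ 12, so chi-square would ordinarily apply. Fisher becomes relevant nearer the ceiling.

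Sparse cells are a fair reason to prefer a simple test, and they count against adjusted logistic regression as the main analysis. They do not count against CMH, which stays simple and has an exact form.

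Finally, the stairs item records a method of climbing and no yes/no rule is visible, and the plan's wording leaves one composite or two outcomes open. Any analysis of these outcomes needs both settled, including the planned one.

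**Conclusion.** The point holds as a missed efficiency in secondary outcomes. A baseline measure of the same items is collected and unused, and a simple stratified test would use it. The size runs from a loss of about 2 points of power to a gain of about 1 point at latent correlations up to 0.4, then +2 to +5 at 0.6 and +8 to +11 at 0.8. It rests on assumed rates and correlations, 35 evaluable patients per arm, a binary preoperative answer and one visit at a time; a joint model over the three visits was not examined. A material gain therefore needs preoperative status to be strongly prognostic. The other benefit, an estimate that accounts for chance preoperative imbalance, does not come from the planned tests. The validity of the trial and its primary analysis is unaffected.

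**What to change.** Replace the chi-square/Fisher sentence in Study Design with:

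> *At each of 2, 6 and 12 weeks, each binary outcome (walking without an assistive device; navigating stairs) will be compared between groups by a Cochran-Mantel-Haenszel test stratified by preoperative status on the same item, using the exact stratified version when expected counts are small, with a stratified risk difference and 95% CI. Raw percentages will also be shown.*

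This treats walking and stairs as two outcomes. State the yes/no definition of stairs ability and apply it identically before surgery and at follow-up. State what counts as a small expected count, so that the choice of test is not left to the analyst. Do not make a likelihood-ratio logistic test the main test, given its over-rejection when nearly all patients are able.

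The change needs no new data. Study Design says that the biostatistician is blinded, so it can be fixed before unblinding. The cost is about 1 to 2 points of power if preoperative status turns out not to be prognostic.
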